### **3. PARTICIPANT SELECTION**

Screening evaluations are detailed in Study Calendar (Section 10). All assessments are to occur within 14 days of Day 1 except where otherwise noted. The participant must be thoroughly informed about all aspects of the study, including the study visit schedule and required evaluations and all regulatory requirements for informed consent. The written informed consent must be obtained from the participant prior to enrollment.

Following registration, any additional laboratory assessments obtained prior to start of treatment will not be used to re-confirm eligibility. Please refer to Section 6 Dosing Delays/Dose Modifications for toxicity management between registration and start of study treatment.

#### **3.1 Eligibility Criteria**

In order to be eligible for participation in this trial, all participants must meet the following criteria on screening examination:

**3.1.1** Have histologically confirmed WHO grade I, II or III meningioma that is progressive or recurrent. Metastatic meningiomas are allowed. Participants with grade I tumors must have failed radiation therapy.

**3.1.2** Prior therapy:

There is no limit on the number of prior surgeries, radiation therapy, radiosurgery treatments or systemically administered therapeutic agents.

For **Cohort 1**: Patients may have been treated with standard external beam radiation or radiosurgery in any combination, however, an interval of  $\geq$  12 weeks (84 days) must have elapsed from the completion of the radiation therapy to start of study therapy unless there is histopathologic confirmation of recurrent tumor or there is new enhancing tumor outside the radiation field (beyond the high dose region or the 80% isodose line). (See Inclusion Criterion 3.1.9 for RT requirements for Cohort 2 patients.)

In addition, there must be subsequent evidence of tumor progression after completion of radiation therapy (grade I tumors only);

An interval of  $\geq$  28 days and full recovery (no ongoing safety issues) from surgical resection ( $\geq$  7 days from stereotactic biopsy).

For prior systemic agents, participants must be at least 4 weeks (or 5 half-lives, whichever is shorter) from other prior cytotoxic chemotherapy (6 weeks from nitrosoureas) or biologic therapies.

**3.1.3** Participants must have recovered to grade  $\leq$  1 or pretreatment baseline from clinically significant adverse events related to prior therapy (exclusions include but are not limited to alopecia, laboratory values listed per inclusion criteria and lymphopenia);

**3.1.4** Be  $\geq$  18 years of age on day of signing informed consent.

CONFIDENTIAL

This document is confidential. Do not disclose or use except as authorized.

**3.1.5** Have a Karnofsky performance status (KPS)  $\geq 70$  (Appendix A).

**3.1.6** Participants must demonstrate adequate organ and marrow function as defined below (all screening labs to be performed within 14 days of treatment initiation):

- White blood cell (WBC)  $\geq 2000/\text{mm}^3$
- Absolute neutrophil count (ANC)  $\geq 1,000/\text{mm}^3$
- Platelet count  $\geq 100,000/\text{mm}^3$
- Hemoglobin  $\geq 9 \text{ gm/dl}$
- AST(SGOT)/ALT(SGPT)  $\leq 3 \times \text{laboratory upper limit of normal (ULN)}$
- Serum creatinine  $\leq 1.5 \times \text{ULN}$   
OR creatinine clearance (measured or calculated)  $\geq 60 \text{ mL/min}$   
for participants with creatinine levels  $> 1.5 \times \text{ULN}$   
*(GFR can be used in place of creatinine or creatinine clearance)*
- Total serum bilirubin  $\leq 1.5 \times \text{ULN}$   
*(except participants with Gilbert's Syndrome, who can have a total bili  $< 5 \times \text{ULN}$ )*
- Resting baseline oxygen saturation  $\geq 92\%$  at rest - by pulse oximetry

CONFIDENTIAL

This document is confidential. Do not disclose or use except as authorized.

**3.1.7** MRI (or CT if MRI contraindicated) within 14 days prior to start of study treatment  
Corticosteroid dose must be stable or decreasing for at least 5 days prior to the scan. If steroids are added or the steroid dose is increased between the date of the screening MRI or CT scan and the start of treatment, a new baseline MRI or CT is required.

**3.1.8** Ability to understand and the willingness to comply with scheduled visits, treatment schedule, laboratory testing, and other requirements of the study, including disease assessment by MRI (or CT), as confirmed by signing a written informed consent document.

**3.1.9** For **Cohort 2**, patients must be a candidate for external beam radiotherapy including either conventional fractionated conformal dosing or stereotactic radiosurgical boost dosing (participants may enroll if they are receiving radiotherapy or have completed it within 12 weeks of starting immunotherapy);

3.1.9.1 For **Cohort 2** patients who are undergoing fractionated conformal re-irradiation to a tumor site that has been previously irradiated, an interval of at least 6 months must have passed since they completed their prior irradiation to be eligible unless the current course of radiation is targeting a new area of tumor growth outside the 80% isodose line of the original radiation field as determined by the treating investigator.

**3.1.10** The effects of nivolumab on the developing human fetus are unknown. For this reason:

3.1.10.1 Women of childbearing potential (WOCBP; defined in Section 3.4) must have a negative serum or urine pregnancy test (minimum sensitivity 25 IU/L or equivalent units of HCG) within 24 hours of starting study therapy;

3.1.10.2 Women must not be breastfeeding;

3.1.10.3 WOCBP must agree to follow instructions for method(s) of contraception from the time of enrollment for the duration of treatment with study therapy plus 5 months after the last dose of Nivolumab.

3.1.10.4 Should a woman become pregnant or suspect she is pregnant while she or her partner is participating in this study, she should inform her treating physician immediately.

3.1.10.5 Men who are sexually active with WOCBP must agree to follow instructions for method(s) of contraception for the duration of treatment with study drug plus 7 months after the last dose of Nivolumab.

3.1.10.6 Investigators shall counsel WOCBP and male subjects who are sexually active with WOCBP on the importance of pregnancy prevention and the implications of an unexpected pregnancy. Investigators shall advise WOCBP and male subjects who are sexually active with WOCBP on the use of highly effective methods of contraception. Highly effective methods of contraception have a failure rate of < 1% per year when used consistently and correctly.

CONFIDENTIAL

This document is confidential. Do not disclose or use except as authorized.

3.1.10.7 At a minimum, subjects must agree to the use of two methods of contraception, with one method being highly effective and the other method being either highly effective or less effective as listed below:

#### HIGHLY EFFECTIVE METHODS OF CONTRACEPTION

- Male condoms with spermicide
- Hormonal methods of contraception including combined oral contraceptive pills, vaginal ring, injectables, implants, and intrauterine devices (IUDs) such as Mirena® by WOCBP subjects or male subject's WOCBP partner. Female partners of male subjects participating in the study may use hormone based contraceptives as one of the acceptable methods of contraception since they will not be receiving study drug
- Progestogen only hormonal contraception associated with inhibition of ovulation
- Intrauterine hormone-releasing system (IUS)
- Nonhormonal IUDs, such as ParaGard®
- Tubal ligation
- Vasectomy
- Complete Abstinence - *Complete abstinence is defined as complete avoidance of heterosexual intercourse and is an acceptable form of contraception for all study drugs. Subjects who choose complete abstinence are not required to use a second method of contraception, but female subjects must continue to have pregnancy tests. Acceptable alternate methods of highly effective contraception must be discussed in the event that the subject chooses to forego complete abstinence.*

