#### UNACCEPTABLE METHODS OF CONTRACEPTION

- Periodic abstinence (calendar, symptothermal, post-ovulation methods)
- Withdrawal (coitus interruptus)
- Spermicide only
- Lactation amenorrhea method (LAM)

**NOTE:** *Azoospermic males and WOCBP who are continuously not heterosexually active are exempt from contraceptive requirements. However, WOCBP participants must still undergo pregnancy testing as described.*

CONFIDENTIAL

This document is confidential. Do not disclose or use except as authorized.

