- a. All screening procedures to be performed within 14 days prior to start of study treatment, except informed consent (which may occur up to 28 days prior to start of study treatment).
- b. C1D1 and Day 1 of subsequent cycles:
  - For C1D1 only, screening assessments may serve as day 1 assessments, except pregnancy test (within 72 hrs of drug) and vital signs & oxygen saturation (within 3 days prior to drug), except in the event that there are any indications that the participant's condition is deteriorating for which laboratory evaluations should be repeated within 48 hrs prior to initiation
  - For all subsequent cycles, required assessments should be performed within 3 days prior to dose.
- c. *Intentionally blank*
- d. End of Tx: End of treatment assessments to be performed within 7 days after last day drug administration or within 7 days after decision to end treatment. Assessments may continue for ongoing reportable adverse events.
- e. 30-Day Post Drug: A contact/visit is to be performed at 30 days (+/-7 days) after date of last study drug administration. This may be performed via documented phone conversation with a study nurse or clinician or a clinic visit. All participants will be followed until resolution or stabilization of any serious or reportable adverse events occurring during treatment or starting within 30 days of last study drug.
- f. Active Follow-Up: Applies only to those pts who did not progress while on study therapy (including pts who start subsequent anti-cancer therapy), until documented disease progression or pt comes off study for some other reason. Participants will be followed every 3 months (+/- 1 month). See footnote x for scan schedule during Active Follow-Up. Once progression is confirmed, participants will enter long-term follow-up.
- g. Participants enter Long-Term Follow-Up after coming off active treatment for disease progression or after completion of Active Follow-Up: Participants will be followed every 3 months (+/- 1 month) via contact or medical record review until death for post-treatment therapies, reason for stopping those therapies, and survival.

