- p. Concomitant medications: concomitant medications (including steroid dose) and reason for administration should be documented in the case history from within 28 days before starting study treatment up to the 30-Day Post Drug Visit.

CONFIDENTIAL

This document is confidential. Do not disclose or use except as authorized.

- q. Adverse event assessment: Adverse events experienced by participants will be collected and recorded from the first dose of study treatment up to the 30-Day Post Drug Visit of the last dose of study medication (+/- 7 days depending on when 30-Day Post Drug visit/contact occurs) and all SAEs (related and unrelated to trial treatment) up to 100 days after the last dose of trial treatment or the start of new anti-cancer treatment, whichever comes first. Afterwards, report only SAEs that are considered related to trial treatment.
- r. Pregnancy Test: For women of child bearing potential, a urine pregnancy test should be performed within 72 hours of first dose of study treatment. If urine pregnancy results cannot be confirmed as negative, a serum pregnancy test will be required.
- s. 12-Lead ECG at screening and as clinically indicated.
- t. Hematology: CBC w/differential, ANC, platelets, Hgb
- u. Serum Chemistry: alkaline phosphatase (ALP), amylase, BUN (or serum urea level), calcium, chloride, creatinine, glucose, LDH, lipase, magnesium, potassium, SGOT (AST), SGPT (ALT), sodium, total bilirubin
  - Hep B/C (HBV sAg and HCV antibody or HCV RNA) will also be performed @ screening only
  - Where required by local regulations, an HIV test must also be performed
- v. Urinalysis via dipstick at screening and to be repeated as clinically indicated.
- w. T3, T4, & TSH: Free T3, Free T4 & TSH @ screening and every 3 cycles (C4D1, C7D1, etc) while on study. NOTE: Thyroid tests do not need to be resulted and reviewed prior to treating but must be reviewed prior to subsequent cycle's dosing (e.g. C4D1 thyroid tests must be reviewed prior to C5D1 dose).
- x. CT alternative, if MRI contraindicated. The same imaging technique should be used in a participant throughout the trial, if feasible. Local reading (investigator assessment) will be used to determine eligibility and for participant management.
  - Baseline scan should be performed within 14 days prior to first dose of study treatment (ideally as close as possible to the date of study therapy initiation).

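### Patient safety: no pregnancy test is scheduled after Cycle 1 Day 1 although dosing is open-ended, and the wording of 3.1.10.7 leaves unclear whether later tests are meant

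*Combined protocol and SAP*

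**What the plan says.** Two statements in Section 3.1.10.7 concern testing of women who need less contraception or none. The entry on complete abstinence, in the list of highly effective methods, says: "Subjects who choose complete abstinence are not required to use a second method of contraception, but female subjects must continue to have pregnancy tests". The NOTE after the unacceptable methods exempts WOCBP who are continuously not heterosexually active from contraception, and adds: "However, WOCBP participants must still undergo pregnancy testing as described". Neither gives a frequency.

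The tests actually described are these:

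- **3.1.10.1:** WOCBP "must have a negative serum or urine pregnancy test" within 24 hours of starting study therapy.
- **Section 10.1, Cohort 1 calendar:** marks at Screening and Cycle 1 Day 1, and blank afterwards.
- **Section 10.2, Cohort 2 calendar:** two marks in the pregnancy-test row.
- **Calendar footnote b, for Cycle 1 Day 1 only:** "screening assessments may serve as day 1 assessments, except pregnancy test (within 72 hrs of drug".
- **Calendar footnote r:** "a urine pregnancy test should be performed within 72 hours of first dose of study treatment", with a serum test if the urine result cannot be confirmed negative.
- **Section 10.3:** a serum test within 72 hours before the initial administration.

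Other safeguards are in Section 3.1.10. Contraception runs "for the duration of treatment with study therapy plus 5 months after the last dose of Nivolumab" (3.1.10.3). At a minimum, "subjects must agree to the use of two methods of contraception, with one method being highly effective" (3.1.10.7). Investigators counsel on pregnancy prevention (3.1.10.6). A woman who is or may be pregnant is told that "she should inform her treating physician immediately" (3.1.10.4). Section 10.3 allows further tests when clinically indicated or needed under local regulations.

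**The concern.** In ordinary use, testing that must *continue* goes on during treatment. A site that follows the calendar exactly would test a woman up to her first dose and never again on schedule, while Section 5.10 sets no limit on treatment duration.

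What is at stake is fetal exposure. Section 3.2.9 treats nivolumab as potentially teratogenic or abortifacient. Pregnancy ends treatment (5.10, 7.5) and must be reported as a serious event (7.2.7, 7.5). Those rules act only once a pregnancy is known. After Cycle 1 Day 1 it becomes known only if the woman or the investigator suspects it, and any doses given before then are not preceded by a test.

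The calendar does write out repeat tests where they are intended: footnote w sets thyroid tests every 3 cycles. For pregnancy there is no such line.

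**Working it through.** **1. Is any test due after the first dose?** The six places listed above all tie testing to screening or first dosing. The column alignment of the Cohort 2 grid cannot be read reliably in the available text, so for that cohort the point rests on footnotes b and r and Section 10.3. The discontinuation and reporting clauses (5.10, 7.2.7, 7.5) say what follows from a pregnancy but schedule no test. Scheduled tests after Cycle 1 Day 1: 0 in Cohort 1 and 0 in Cohort 2.

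**2. Two readings of 3.1.10.7.**

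- *On-treatment testing is required.* The calendar then does not deliver it.
- *Abstinence or sexual inactivity does not waive the tests described elsewhere.* Text and calendar then agree, because the described tests stop at the first dose.

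Both readings leave the count in step 1 at 0.

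**3. Doses without a scheduled test, per woman, first 26 weeks (182 days) of Cohort 2.** Inputs: Table 5.2, Dose Level 0 (four combination doses 3 weeks apart, then nivolumab every 4 weeks), and the 24-day minimum between ipilimumab doses in Section 5.2.4 and footnote jj. Dosing windows are otherwise ignored.

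- *3-weekly plan.* Weeks 0, 3, 6, 9, then 12, 16, 20, 24 (or 13, 17, 21, 25): 8 doses, so 8 − 1 = 7 after Cycle 1 Day 1. The last falls 24 or 25 weeks after the last scheduled test.
- *24-day minimum applied, maintenance 28 days after the fourth dose.* Days 0, 24, 48, 72, then 100, 128, 156. The next would be day 184, outside the window. That is 7 doses, so 7 − 1 = 6 after Cycle 1 Day 1. The last falls 156 / 7 = 22.3 weeks after the last scheduled test.

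The range is therefore 6 to 7 later doses, with 0 scheduled tests.

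**4. Cohort 1.** Section 1 has Cohort 2 enrolling only after Cohort 1 is full, so a change reaches only Cohort 1 women still on treatment. For them, each further 26 weeks holds 182 / 14 = 13 doses at 2-weekly dosing, or 182 / 28 = 6.5, that is 6 or 7, at 4-weekly dosing. Again 0 tests are scheduled.

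**5. The pre-dose test itself.** The window is 24 hours in 3.1.10.1 but 72 hours in footnotes b and r and in 10.3. The specimen is serum or urine in 3.1.10.1, urine first in footnote r, and serum in 10.3. Editing footnote r and 10.3 without settling this would leave sites with three versions.

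**The case against.** The strongest reply is that nothing is inconsistent. The abstinence sentence is about what abstinence excuses, and the NOTE sends the reader to testing *as described*, which creates no new schedule. This stands: the second reading is reasonable, and the documents do not rule it out. A reader might infer that the protocol orders on-treatment testing and then fails to schedule it. The text is too ambiguous to support that.

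It can also be said that the women named in 3.1.10.7 are those least likely to conceive, and that nothing in the documents supports a 4-week interval or testing of all WOCBP. Both are fair. The wider coverage has to be argued as a safety improvement, because the text does not require it.

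Third, safeguards exist beyond contraception and self-report. A clinician examines each woman at the start of every cycle (footnote l), and adverse events are sought by open questioning at each visit (7.2.3). These are real, but they depend on suspicion and do not replace a test.

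Finally, the dose counts describe the schedule, not harm. Section 2.1 says that meningioma incidence rises with age, and each cohort has about 25 patients, so WOCBP may be few. That also stands.

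**Conclusion.** This is a cheap patient-safety improvement, not a proven contradiction. After Cycle 1 Day 1 no pregnancy test is scheduled in either cohort, whichever way 3.1.10.7 is read, and treatment is open-ended.

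In Cohort 2 at Dose Level 0 this means 6 to 7 doses per woman in the first 26 weeks, the last of them about 22 to 25 weeks after the last scheduled test. The count assumes planned dosing days with no delays. In Cohort 1 it matters only for women still on treatment.

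A reader might infer that a known group of women is dosed unprotected. The documents do not support that: contraception, counselling, self-report and clinically indicated testing are all provided for, and the number of women affected cannot be estimated and could be zero. The primary endpoint, sample size and analysis are untouched.

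**What to change.** In both calendars, footnote r and Section 10.3, add a urine pregnancy test for WOCBP at dosing visits that already take place:

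- **Cohort 2:** Day 1 of each cycle.
- **Cohort 1, women still on treatment:** every second 2-weekly cycle, or each dose after the switch to 4-weekly dosing.
- **Both cohorts:** one test at End of Treatment, to find a pregnancy exposed to the last doses and report it under 7.5.

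Keep the serum test when the urine result cannot be confirmed negative. Have the abstinence entry and the NOTE in 3.1.10.7 refer to this schedule by name. In the same amendment, set one pre-dose window and one specimen rule across 3.1.10.1, footnotes b and r, and 10.3. If the sponsor wants only the minimum, the schedule should at least cover the women named in 3.1.10.7.

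Each dose in Cohort 2 and on 4-weekly dosing would then have its own test, and on 2-weekly dosing no dose would come more than 2 weeks after one. No test after End of Treatment is proposed, since no dose is left to withhold.

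The cost is a short amendment and no new visits. Per woman, Cohort 2 adds 6 to 7 tests in the first 26 weeks plus 1 at End of Treatment, so 7 to 8. Cohort 1 adds 6 to 7 per 26 weeks of remaining treatment plus 1, also 7 to 8. An occasional dose would wait for serum confirmation.

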#### LESS EFFECTIVE METHODS OF CONTRACEPTION

- Diaphragm with spermicide
- Cervical cap with spermicide
- Vaginal sponge
- Male Condom without spermicide
- Progestin only pills by WOCBP subjects or male subject's WOCBP partner
- Female Condom - *A male and female condom must not be used together*

#### UNACCEPTABLE METHODS OF CONTRACEPTION

- Periodic abstinence (calendar, symptothermal, post-ovulation methods)
- Withdrawal (coitus interruptus)
- Spermicide only
- Lactation amenorrhea method (LAM)

**NOTE:** *Azoospermic males and WOCBP who are continuously not heterosexually active are exempt from contraceptive requirements. However, WOCBP participants must still undergo pregnancy testing as described.*

CONFIDENTIAL

This document is confidential. Do not disclose or use except as authorized.

### 3.2 Exclusion Criteria

The participant must be excluded from participating in the trial if s/he meets any of the following criteria:

- 3.2.1 Current or planned participation in a study of an investigational agent or using an investigational device;
- 3.2.2 Tumors that are primarily localized within the brainstem or spinal cord;
- 3.2.3 Evidence of intratumoral or peritumoral hemorrhage on baseline MRI scan other than those that are grade  $\leq 1$  and either post-operative or stable on at least 2 consecutive MRI scans;

#### 3.2.4 Prior Therapy:

- 3.2.4.1 Prior treatment with systemic immunosuppressive treatments, aside from systemic dexamethasone therapy for cerebral edema, such as methotrexate, chloroquine, azathioprine, etc. within 3 months of start of study therapy;
- 3.2.4.2 Prior treatment with interstitial brachytherapy within 6 months of start of study therapy;
- 3.2.4.3 **All patients:** Previous treatment with PD-1 or PD-L1 directed therapy;
- 3.2.4.4 **Cohort 2 patients:** Previous treatment with CTLA-4 directed therapy;
- 3.2.4.5 Surgical procedure (including open biopsy, surgical resection, wound revision, or any other major surgery involving entry into a body cavity) or significant traumatic injury within 28 days prior to first study treatment, or anticipation of need for major surgical procedure during the course of the study;
- 3.2.4.6 Minor surgical procedure (eg, stereotactic biopsy within 7 days of first study treatment; placement of a vascular access device within 2 days of first study treatment);

